1.0 Objectives

1.1 Describe the purpose, specific aims, or objectives of this research.

Response:

The purpose of this project is to develop and test affordable, effective strategies to reduce caregiver burden and associated negative effects (e.g., depression and fatigue) and to increase caregivers' satisfaction and self-efficacy, so that they can continue providing home-based care to their care recipients (CRs) who are members of the Program of All-inclusive Care for the Elderly (PACE). This project will connect PACE organizations and university occupational therapy (OT) graduate level curriculum to produce a practical, sustainable care model. In this project, a research component pertains to assess effectiveness of OT interventions

1.2 State the hypotheses to be tested, if applicable.

NOTE: A hypothesis is a specific, testable prediction about what you expect to happen in your study that corresponds with your above listed objectives.

Response:

We have three reteach questions and two hypotheses.

1. What are challenges that caregivers are facing in caring for their care recipients?
2. Which solutions were accepted and effective?
3. The intervention group will reduce caregiver burden and depression, while the control group will not.
4. The intervention group will increase the scores of positive aspect of caregiving and self-efficacy while the control group will not.
5. At 6-months after intervention, does the effect of our intervention exist?

In addition, we will identify the rate of care recipients who live in the community opposed to moving to a nursing home for both groups, and the number of falls and emerveny visits of care recipients.

Scientific Endpoints

2.1 Describe the scientific endpoint(s), the main result or occurrence under study.

*NOTE: Scientific endpoints are outcomes defined before the study begins to determine whether the objectives of the study have been met and to draw conclusions from the data. Include primary and secondary endpoints. Some example endpoints are: reduction of symptoms, improvement in quality of life, or survival. Your response should **not** be a date.*

Response:

Primary endpoint for the study is the reduction of caregiver burden and depression. Secondary endpoints is the improvement in positive aspect of caregiving and self-esteem.

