4.0 Local Number of Subjects

4.1 Indicate the total number of subjects that will be enrolled or records that will be reviewed locally.

Response: 60

4.2 If applicable, indicate how many subjects you expect to screen to reach your target sample (i.e. your screen failure rate).

Response: 75

4.3 Justify the feasibility of recruiting the proposed number of eligible subjects within the anticipated recruitment period. For example, how many potential subjects do you have access to? What percentage of those potential subjects do you need to recruit?

Response:

There are approximately 300 PACE enrollees/members in Eire and Niagara Counties. Among them 50% are having cognitive impairments. Of 150, we expect about 1/2 to 2/3 of them have caregivers who are experiencing challenges in caregiving; therefore 75 to 100 caregivers. The sample size for this study was determined by a power analysis based on the study similar to ours (Kamiya et al., 2014). The effect size found in the article was $d = 0.65$. We will use a directional hypothesis; therefore, we set $\alpha = .05$, and in order to achieve 80% of statistical power, we will need 30 participants in each group, therefore 60 in total. Expecting 25% attrition, we will recruit 75 participants.

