A month after initial assessment, OTGS will contact CRs for follow-up and 2 months later, the posttest will be administered. At 4 months, follow-up interview will occur. The number of home visits (4-6) will vary depending on case. Finally 6 months after the intervention, a phone call will be made, asking the same questions before and the number of falls and emergency visits of care recipients in the past 10 months. After each interview, a participant will be paid \$20. (The total maximum is \$80).

9.2 Describe what data will be collected.

NOTE: For studies with multiple data collection points or long-term follow up, consider the addition of a schedule or table in your response.

Response:

The outcome measures will use established instruments. To measure caregiver burden, 12-item Zarit Burden Interview (ZBI), for depression, 20-item Center for Epidemiology Study-Depression (CES-D) will be used. Positive Aspect of Caregiving has 9 items. Self-esteem and fatigue questions will use a visual analog scale from 1 to 10. In addition, items of activities of daily living (ADL, e.g., eating, dressing, and toileting) and instrumental ADL (IADL, e.g., meal preparation, housekeeping) that caregivers are assisting will be identified. We do not assess or provide interventions for CRs directly, but we ask caregivers about CR's cognitive levels using Global Deterioration Scale, and functional levels using FIM to assess ADL and OARS' IADL. We also ask if care recipients fell or visited an emergency room.

 *9.3 List any instruments or measurement tools used to collect data (e.g. questionnaire, interview guide, validated instrument, data collection form).*

Include copies of these documents with your submission.

Response:

The assessment form is attached.

9.4 Describe any source records that will be used to collect data about subjects (e.g. school records, electronic medical records).

Response:

We will not use other sources or records. But if the cause of cognitive impairment is not clear, we will ask the PACE to provide it for us. This is written in the consent form.

*9.5 Indicate whether or not **individual** subject results, such as results of investigational diagnostic tests, genetic tests, or incidental findings will be shared with subjects or others (e.g., the subject's primary care physician) and if so, describe how these will be shared.*

Response:

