16.0 Data Management and Analysis

16.1 *Describe the data analysis plan, including any statistical procedures. This section applies to both quantitative and qualitative analysis.*

Response:

For two hypotheses, we first analyze a linear trend of dependent variables over time. If they are linear, we will use Generalized Estimating Equation to compare the two groups' slopes. A main effect and an interaction effect will be examined. If it is not, we will use Repeated Measures ANOVA with a between-factor. The contrasts within a group and the difference between groups will be performed as post hoc tests. To answer the last research question to find the difference between

the 4-months data and 6 month after intervention (or at 10 months), we will use Repaeated measurs ANVA with a between-factor.

To answer research questions, we will list all challenges for both groups and solutions for the treatment group. The effectiveness of solutions will be evaluated using a Likert Scale (from very effective to not effective at all) and percentages will be reported. For the rate of continued community, living at 4 months will be tabulated for both groups and a chi-square test will be used. The number of falls and emergency visits will be compared for these two groups using Mann Whitney U-test.

The significance level for primary analyses will be set at .05. SPSS 26.0 will be used for statistical analyses.

16.2 If applicable, provide a power analysis.

NOTE: This may not apply to certain types of studies, including chart/records reviews, survey studies, or observational studies. This question is asked to elicit whether the investigator has an adequate sample size to achieve the study objectives and justify a conclusion.

Response:

The sample size for this study was determined by a power analysis based on the study similar to our study (Kamiya et al., 2014). The effect size found in the article was $d = .65$. We will use a directional hypothesis; therefore, we set $\alpha = .05$, and in order to achieve 80% of statistical power, we will need 30 participants in each group, therefore 60 in total. Expecting 25% of attrition, we will recruit 75 participants.

16.3 Describe any procedures that will be used for quality control of collected data.

Response:

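### Burden and depression are both primary at .05 with no rule for success, while the 30 per group reproduces as one one-sided test

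*Combined protocol and SAP*

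**What the plan says.** All references are to the combined protocol and SAP.

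- **Endpoints.** Under Scientific Endpoints, item 2.1: "Primary endpoint for the study is the reduction of caregiver burden and depression". Hypothesis 3 in section 1.2 has the same form: "The intervention group will reduce caregiver burden and depression, while the control group will not".
- **Instruments.** Section 9.2: "To measure caregiver burden, 12-item Zarit Burden Interview (ZBI), for depression, 20-item Center for Epidemiology Study-Depression (CES-D) will be used". No composite of the two scales is defined.
- **Sample size.** Sections 4.3 and 16.2 take a single d = 0.65 from a cited study, a directional hypothesis and alpha .05, and conclude that "in order to achieve 80% of statistical power, we will need 30 participants in each group". Neither section names the outcome to which d belongs.
- **Analysis.** If the trend over time is linear, section 16.1 says "we will use Generalized Estimating Equation to compare the two" groups' slopes, and adds: "A main effect and an interaction effect will be examined". For a non-linear trend: "If it is not, we will use Repeated Measures ANOVA with a between-factor". Within-group contrasts and between-group differences are classed as post hoc. The level for primary analyses is .05.

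No section says whether one or both primaries must succeed, in what order they are tested, or how alpha is shared. None says which effect decides the result for each primary.

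**The concern.** With two primary endpoints on two scales, the trial can end with one significant and the other not. A reader who requires both would call that a failure. A reader who accepts either would call the same data a success. The plan does not choose between them, so the choice could be made after the results are seen.

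The stated 80% power and .05 level also cannot both be taken at face value for the pair of endpoints. Requiring both keeps the error rate but lowers the power. Accepting either without adjustment raises the error rate. Section 16.1 leaves further room by listing a main effect and an interaction without saying which one is confirmatory.

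**Working it through.** **Inputs from the plan (4.3, 16.2):** d = 0.65, one-sided alpha .05, 30 per group. The tests are taken as one-sided because the sample-size text calls the hypothesis directional.

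**Assumed, because the documents do not give them:** d = 0.65 on both endpoints; between-endpoint correlation ρ from 0 to 0.9; 30 completers per group.

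**1. Reproduce the plan's figure.** Two-sample t test, df = 58, critical value 1.672, noncentrality 0.65 × √(30/2) = 2.517. Power is P(T > 1.672) under the noncentral t = 0.8004. Solving for n gives 29.97, so 30. At one-sided .025 the same 30 per group gives 69.7%. The plan's figure is therefore one one-sided .05 test, with no allowance for a second endpoint.

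**2. Apply the possible rules.** The power columns come from 200,000 simulated pairs of two-sample t tests. *Exactly one* is *at least one* minus *both*. The error column is 1 − Φ₂(1.645, 1.645; ρ) with no effect on either endpoint.

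| ρ | Both significant | At least one | Exactly one | False-positive rate if either suffices |
|---|---|---|---|---|
| 0 | 63.9% | 95.9% | 32.0% | 9.75% |
| 0.3 | 66.9% | 93.5% | 26.6% | 9.29% |
| 0.5 | 68.7% | 91.4% | 22.8% | 8.78% |
| 0.7 | 71.3% | 88.8% | 17.5% | 8.04% |
| 0.9 | 75.2% | 85.2% | 10.0% | 6.81% |

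Checks at ρ = 0: 0.8004² = 0.641 for both, which agrees within simulation error, and 1 − 0.95² = 0.0975 for the either-rule. When both are required, the type I error cannot exceed .05, because the endpoint without an effect must itself pass a .05 test.

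**3. Rules that hold .05 without requiring both.**

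- Fixed order: the first endpoint keeps the power of step 1. The second is claimed only when both are significant, so in 64-75% of trials.
- Holm: at least one endpoint is significant in 90.8% (ρ = 0) to 76.1% (ρ = 0.9) of trials. Power per endpoint is 77.0% to 74.2%, against 80.0% unadjusted.

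**4. Limit of these figures.** They belong to the simple two-sample test. Power of the slope comparison or the ANOVA also depends on the correlation r between visits, the shape of the effect over time, and whether d refers to raw or change scores. The documents give none of these. For illustration, take d in raw SD units and a first-to-last change contrast, so that d becomes 0.65/√(2(1 − r)):

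| Assumed r | Effective d | Power, one endpoint | Power, both (ρ 0 to 0.9) |
|---|---|---|---|
| 0.3 | 0.549 | 68% | 46-61% |
| 0.5 | 0.650 | 80% | 64-75% |
| 0.7 | 0.839 | 94% | 89-92% |

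Power under the planned analysis could therefore lie on either side of the two-sample figure.

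**The case against.** The strongest reply is that the plan already implies a rule. Item 2.1 speaks of one endpoint, burden and depression are joined by a conjunction, and hypothesis 3 is a single statement about both. On that reading no multiplicity adjustment is needed. This largely stands. A reader might infer that the plan inflates its false-positive rate to nearly 10%, but that needs an either-rule that no section states. What remains on the conjunctive reading is that the 80% in the sample-size sections is not the power to succeed on both, and that the rule is implied rather than stated.

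A second reply is that each endpoint may support its own claim. Then .05 and 80% hold for each test, but the chance of at least one false claim is again 6.8-9.75% when neither effect exists, and the plan does not say that this is intended.

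A third reply is that the repeated-measures analysis may have more power than a two-sample test. It may, or it may have less (step 4). A reader should not infer from 64-75% that the planned analysis has that power, nor that it reaches 80%. More power would make split results rarer but would not supply the missing rule.

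Finally, a reader might infer that the study was sized for burden alone, since the title of the cited article mentions only burden. The power sections name no outcome, so even sizing for one endpoint is an inference from the single d and the arithmetic. The same n would fit 80% power for each endpoint taken separately.

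**Conclusion.** The point holds as a missing decision rule whose consequences depend on the reading. Two outcomes are primary at .05, and the stated sample size supports one one-sided two-sample test. If both must succeed, which the wording favours, the error rate is controlled and power is about 64-75%, not 80%. If either suffices unadjusted, the false-positive rate is about 6.8-9.75%. On any reading, about 10-32% of trials would give a split result that the plan does not tell the reader how to judge.

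The figures rest on the plan's own two-sample calculation with 30 completers per group and ρ between 0 and 0.9. The power and split-result figures also assume d = 0.65 on both endpoints. They are not estimates of power for the GEE or the ANOVA. Whether the trial will have 30 completers per group (the attrition arithmetic, and the 60 and 75 given in section 4.0) is a separate issue.

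**What to change.** Amend item 2.1 and section 16.1 before the data are analysed.

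1. **State the success rule.** Test the two primaries in a fixed order chosen by the sponsor, each at one-sided .05, the second only if the first is significant. Alternatives are Holm across the two, or requiring both and restating the power as about 64-75% on the two-sample calculation.
2. **Name one confirmatory test per primary:** a single-degree-of-freedom, directional between-group contrast in change. In the GEE this is the group-by-time slope. In the ANOVA fallback it should be a pre-specified between-group contrast of change from baseline at one named visit. The omnibus interaction will not serve: with two groups and at least three visits it is an F test on at least (2 − 1) × (3 − 1) = 2 degrees of freedom, and it has no direction.
3. **Label as descriptive** the main effect, the within-group contrasts and the other post hoc between-group differences.

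The amended text should not promise 80% power for the first endpoint under the GEE or ANOVA. That figure applies only to the simple two-sample test with 30 completers per group.

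The cost is wording, with no added participants. Under a fixed order, the second endpoint cannot be claimed if the first fails. Holm lowers power per endpoint to about 74-77% on the two-sample calculation. Requiring both lowers the stated power.

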2.0 Background

2.1 Provide the scientific or scholarly background, rationale, and significance of the research based on the existing literature and how it will contribute to existing knowledge. Describe any gaps in current knowledge. Include relevant preliminary findings or prior research by the investigator.

Response:

Current research shows that caregiver burden is an issue of concern for this population, as the depression that often accompanies burden can be debilitating for caregivers (Dean & Wilcock, 2017; Etters, Goodall, & Harrison, 2007). When caregivers experience high levels of burden, their care recipients are much more likely to be placed in a nursing home (Etters, Goodall, & Harrison, 2007). Levels of caregiver burden are higher if care recipients have dementia (Prinquart & Sorensen, 2007), because these caregivers face more difference challenges than caregivers for older adults without dementia. Caregiver burden tends to be the result of care of a recipient who has impairments in function, behavior, cognition, and/or psychological factors such as depression (Paradise et al., 2014).

Caregivers are often unaware of how to provide care for their care recipients when they are struggling with the symptoms of AD, especially when they are having difficulty with activities of daily living (ADLs : Seehaer, Low, Reppermund, & Brodaty, 2013). Providing support, education, and training to caregivers that address their individual challenges has the potential to decrease the burden felt by caregivers and as a result increases both the caregivers and care recipients quality of life.

Current research identifies specific interventions that are effective. Pharmacological drug interventions for the care recipient have been shown to relieve caregiver burden (Beinart, et. al., 2012). This information, although helpful for understanding the population, is more specific to

addressing the medical needs of the care recipient rather than the caregiver. Another finding from previous research is that interventions that are individually customized to the care recipient and caregiver's needs are more effective than generalized interventions (Pinquart & Sørensen, 2006). There are interventions and educational programs for caregivers that have shown to be effective (Austrom & Lu, 2009). Support groups are effective to help caregivers, but currently no program supports caregivers by instructing how to provide care for care recipient's ADLs, which is the core of caregiving tasks. Occupational therapist (OT) can apply their knowledge in providing care for patients with dementia to caregivers. In doing so, we realize that practical solutions for the challenges that caregivers are facing can be developed using a caregiver-centered approach, rather than a top-down approach. Therefore, individualized interventions for the caregiver determined on a case-by-case basis by a team of gerontologists, occupational therapists, and occupational therapy students, which can be finalized by the input from caregivers, may lead to a better outcome for caregiving situations. In addition we explore if positive effects of caregiver support will last six months after the intervention because it will find if continuous support is needed for this target population. Currently, related studies do not exist.

2.2 Include complete citations or references.

2.3

Response:

Austrom M G, & Lu, Y. (2009). Long term caregiving: helping families of persons with mild cognitive impairment cope. *Current Alzheimer Research*, 6 (4), 392-398.

Dean K & Wilcock G. (2012) living with mild cognitive impairment: the patient's and carer's experience. *International Psychogeriatrics*, 24(6), 871-881.

3.0 Study Design

3.1 Describe and explain the study design (e.g. case-control, cross-sectional, ethnographic, experimental, interventional, longitudinal, observational).

Response:

We will use a qualitative method to understand difficulties that caregivers are facing and to document solutions and their implementation process; and a quantitative method using a randomized contoured trial with pre-, post- and follow-up experimental design. A treatment group will receive a 1 to 2-month interventions to solve caregiving challenges, and a control group will receive usual support. Assessments will be conducted at baseline, 2 months (posttest), 4 months (follow-up), and 6 months post intervention.

4.0 Local Number of Subjects

4.1 Indicate the total number of subjects that will be enrolled or records that will be reviewed locally.

Response: 60

4.2 If applicable, indicate how many subjects you expect to screen to reach your target sample (i.e. your screen failure rate).

Response: 75

4.3 Justify the feasibility of recruiting the proposed number of eligible subjects within the anticipated recruitment period. For example, how many potential subjects do you have access to? What percentage of those potential subjects do you need to recruit?

Response:

There are approximately 300 PACE enrollees/members in Eire and Niagara Counties. Among them 50% are having cognitive impairments. Of 150, we expect about 1/2 to 2/3 of them have caregivers who are experiencing challenges in caregiving; therefore 75 to 100 caregivers. The sample size for this study was determined by a power analysis based on the study similar to ours (Kamiya et al., 2014). The effect size found in the article was $d = 0.65$. We will use a directional hypothesis; therefore, we set $\alpha = .05$, and in order to achieve 80% of statistical power, we will need 30 participants in each group, therefore 60 in total. Expecting 25% attrition, we will recruit 75 participants.

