8.0 Recruitment Methods

N/A: This is a records review only, and subjects will not be recruited. NOTE: If you select this option, please make sure that all records review procedures and inclusion/exclusion screening are adequately described in other sections.

8.1 Describe when, where, and how potential subjects will be recruited.

NOTE: Recruitment refers to how you are identifying potential participants and introducing them to the study. Include specific methods you will use (e.g. searching charts for specific ICD code numbers, Research Participant Groups, posted advertisements, etc.).

Response:

An invitation letter will be mailed to all caregivers of PACE enrollees who have cognitive impairment from the PACE. (The letter is attached.) Caregivers who are interested in the study will return the letter to the PI.

8.2 Describe how you will protect the privacy interests of prospective subjects during the recruitment process.

NOTE: Privacy refers to an individual's right to control access to him or herself.

Response:

Caregivers who are interested in the study will contact the PI. They will not be able to stop receiving the invitation letter from the PACE, but they control access to them by contacting or not contacting the PI; therefore their privacy is protected.

8.3 Identify any materials that will be used to recruit subjects.

NOTE: Examples include scripts for telephone calls, in person announcements / presentations, email invitations.

 For advertisements, include the final copy of printed advertisements with your submission. When advertisements are taped for broadcast, attach the final audio/video tape. *NOTE: You may submit the wording of the advertisement prior to taping to ensure there will be no IRB-required revisions, provided the IRB also reviews and approves the final version.*

Response:

The invitation letter and a flyer are attached. They will be mailed together.

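### Sections 4.1 to 4.3 and 16.2 give 60 and 75 conflicting meanings, and 75 recruits allow for 20% attrition, not the stated 25%

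*Combined protocol and SAP*

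**What the plan says.** Section 4.3 bases the sample size on d = 0.65 from an earlier study, alpha .05 and 80% power. It declares the direction of the test ("We will use a directional hypothesis") and arrives at 30 per group, 60 in total. It then adds "Expecting 25% attrition, we will recruit 75 participants". Section 16.2 repeats the calculation and ends in almost the same words: "Expecting 25% of attrition, we will recruit 75 participants".

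Two short answers earlier in Section 4.0 use the same two numbers differently. Section 4.1, which asks for the total to be enrolled, answers 60. Section 4.2, which asks how many must be screened to reach the target, answers 75.

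Section 4.3 estimates the available pool ("therefore 75 to 100 caregivers"). Section 18.3 says that data collected before a withdrawal are kept and analysed.

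**The concern.** Two things do not fit.

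First, attrition normally means the share of those who start and are then lost. The allowance is therefore found by dividing the required number by the share retained. The protocol's 75 comes instead from adding 25% to 60.

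Second, 60 is both the number enrolled (4.1) and the number needed after losses (4.3, 16.2). Likewise 75 is both the number screened (4.2) and the number recruited (4.3, 16.2). The same 15 people cannot be both screening failures and dropouts.

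The 80% power is the stated justification for the sample size, and 4.1 is the enrolment figure given to the IRB. As written, a reader cannot tell whether 60 or 75 caregivers will be randomised, or whether any allowance for dropout remains.

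**Working it through.** **Inputs** (Sections 4.1 to 4.3, repeated in part in 16.2): d = 0.65; alpha .05, one-sided because the hypothesis is directional; power 80%; 30 per arm; attrition 25%; 75 recruited; 60 enrolled; 75 screened. No test is named, so a two-sample t test with equal arms is an inference. It is checked in step 1.

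**1. Reproduce the protocol's 30 per arm.** The normal approximation is n = 2(z₀.₉₅ + z₀.₈₀)²/d² = 2(1.645 + 0.842)²/0.65² ≈ 29.3, so 30. The noncentral t calculation gives 29.97, also 30, with power of 80.0% at 30/30. The inferred test therefore matches the protocol's figure.

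**2. Attrition allowance.**
- How 75 arises: 60 × 1.25 = 75.
- What 25% attrition leaves: 75 × 0.75 = 56.25, about 56, or 28 per arm.
- What 75 covers: 1 − 60/75 = 20%.
- What 25% would need: 60/0.75 = 80.

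**3. Consistency of the counts.** There are three ways to read them together:

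| Reading | Consequence |
|---|---|
| 75 screened, 75 enrolled | No screening failures allowed for (0%), and 4.1 should not say 60 |
| 75 screened, 60 enrolled | 15/75 = 20% screening failure; nothing left for attrition |
| 75 recruited only in the form template's sense (8.1: "Recruitment refers to how you are identifying potential participants and introducing them to the study") | Agrees with 75 screened, but attrition is again uncovered |

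None of them makes all four sections and the 25% agree.

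**4. Power on the quoted calculation.** Power = P(T > t₀.₉₅,df), where T is noncentral t with df = n₁ + n₂ − 2 and noncentrality d·√(n₁n₂/(n₁ + n₂)).

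| Case | Completers | Power | d detectable with 80% power |
|---|---|---|---|
| As required | 60 (30/30) | 80.0% | 0.65 |
| 75 enrolled, 25% lost | 56 (28/28) | 77.5% | 0.67 |
| 60 enrolled, 25% lost (60 × 0.75) | 45 (22/23) | 69.2% | 0.75 |

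The loss is 80.0 − 77.5 = 2.5 points if 75 are enrolled. It is about 10.9 points (80.04 − 69.16) if 60 are enrolled.

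**The case against.** The best defence has three parts.

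*The slip is small, and the wording can be stretched to fit.* If 25% is taken as a share of the 60 required, 15 extra gives exactly 75. The text does not define attrition that way and it is not the usual meaning, but the objection is fair on size: 4 completers and 2.5 points of power.

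*The planned analysis is not a complete-case t test.* This stands. Section 16.1 begins with "For two hypotheses, we first analyze a linear trend of dependent variables over time" and uses generalised estimating equations if the trend is linear. With 18.3 keeping data up to withdrawal, a caregiver lost after an early assessment still contributes. The repeated-measures ANOVA fallback may not gain from this. The effect cannot be sized, because the documents give no within-subject correlation. As an illustration only, assume a baseline-to-outcome correlation of 0.3 to 0.7 with 28 per arm. A baseline-adjusted comparison would then have about 81% to 96% power, and a change-score comparison about 65% to 93%. A reader might infer that the trial as planned misses 80% power. The documents do not support that; they show only that the quoted calculation does.

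*The larger loss is one branch.* A reader might also infer that the trial will run at about 69% power. That requires the 60 in 4.1 to override two explicit statements that 75 will be recruited, and nothing in the documents says that it does.

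None of this reconciles 4.1 and 4.2 with 4.3 and 16.2.

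**Conclusion.** The point holds in limited form. The count conflict is the main finding: the four sections cannot all be right as written, and the enrolment number is unsettled. The attrition slip is certain as arithmetic but minor by itself.

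The 77.5% (75 enrolled) and the 69% (only if 60 are enrolled) rest on d = 0.65, a one-sided .05 level, equal arms, a t test inferred from its match to 30 per arm, and complete loss of information from dropouts. They test the protocol's stated justification. The size, and even the existence, of a shortfall in the planned longitudinal analysis is unknown.

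**What to change.** Keep 75 recruited. In both 4.3 and 16.2, do one of the following:
- state that 75 allows for 20% attrition; or
- keep 25% and restate power as about 78%, one-sided, at 56 completers.

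Then make the screened, enrolled and completing numbers agree across 4.1, 4.2, 4.3 and 16.2. If 75 are to be enrolled, 4.1 should say 75 and 4.2 a larger number.

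Recruiting 80 would also preserve 60 after a 25% loss, but it is 80% (80/100) to 107% (80/75) of the pool expected in 4.3, against 75% to 100% for 75. That pool is not a firm ceiling: under 8.1 letters go to all caregivers of enrollees with cognitive impairment, and 4.3 puts those enrollees at about 150. Screening more than 75 also passes its low end, so the feasibility statement in 4.3 should be checked against the new screening number.

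**Cost.** If 75 was always the intended enrolment, the change is wording only. The first option means a less cautious dropout assumption, the second a slightly lower stated power. If 60 was the true enrolment, moving to 75 is a change for the IRB: 15 more participants and up to 15 × $80 = $1,200 in payments. Section 9.1 adds "The number of home visits (4-6) will vary depending on case", so there would be at most 15 × 4 = 60 to 15 × 6 = 90 further visits. That may be too high, because 9.1 does not split visits by arm and controls receive usual support.
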